5.2 INTERVENTION

Not applicable.

5.3 PROCEDURES

Patients who meet all inclusion criteria will undergo the study related procedures stated below.

During enrollment, FH IDS will assign medication to patients in order of enrollment and according to the randomization code list. The patient will then receive medication dispensed from the bottle with the corresponding study ID.

Patient treatment will follow (section 5.1).

Following surgery, patients will be admitted to the hospital and a basic standardized treatment pathway will be initiated.

- 1) Following surgery patients are admitted with NPO status, PRN IV opioid pain medication, and PRN IV anti-nausea medication.
- 2) Epidural use is up to the discretions of the treating surgeon.
 - a. Non-narcotic adjuncts can be used as determined by the physician

- 3) Nasogastric tubes are NOT routinely left in following surgery. However, nasogastric tube use is up to the discretion of the treating surgeon. Patients who require NGT will be excluded from the study.
- 4) Patients remain NPO until the following criteria are met: reported flatus, absence of nausea and/or emesis and/or bloating, and absence of abdominal distention. Alternatively, clinical determination made by the physician can be utilized for diet advancement. If clinical determination outside of these parameters is used then the justification for the clinical decision making will be recorded for these patients.
- 5) Transition to oral pain medication will occur at or after the time of transition to clear liquids.
- 6) Diet advancement after clears will occur at physician discretion
- 7) Minimum discharge criteria include: toleration of diet beyond clears, toleration of oral pain medication, and absence of nausea/vomiting/distention.
 - a. Toleration of solid food is NOT required for discharge
 - b. Production of a bowel movement is NOT required for discharge

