3 STUDY OBJECTIVES AND ENDPOINTS

3.1 STUDY OBJECTIVES

3.1.1 PRIMARY OBJECTIVES:

Primary Objective: To investigate the efficacy and safety of Almimopan, 12mg, administered orally 30 to 90 minutes preoperatively and twice daily postoperatively for a maximum of 7 days (15 total doses) in conjunction with a standardization postoperative care pathway for managing postoperative ileus after ventral hernia repair.

3.1.2 SECONDARY OBJECTIVES:

Secondary Objective: To investigate the post-operative gastrointestinal recovery, and treatment related morbidity after ventral hernia repair.

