4.3.3 SAMPLE SIZE DETERMINATION

A total of 140 patients are expected to undergo research related treatments. The study will contain one open surgery arm. The open surgery arm will be a single-site prospective, randomized, double-blinded, placebo-controlled clinical trial with 1:1

randomization between the study drug and placebo with 70 patients in each group for a total of 140 patients in the study. An interim evaluation of efficacy will be conducted separately in the open surgery arm when half the patients have been recruited.

This study is expected to enroll up to 140 subjects from one academic medical center (Froedtert Hospital and the Medical College of Wisconsin) a site that performs state of the art hernia repairs and is a high volume hernia practices.

The study has been designed to provide at least 80% power to detect a 24-hour decrease in the time to return of bowel function in the treatment group compared to the control group at a one-sided 2.5% significance level. This corresponds to a two-sided 5% significance level, but acknowledges the one-sided nature of the study hypothesis. Based on data from studies of the experimental treatment in other contexts, as well as internal data, we expect a standard deviation of 48 hours. Adjusting for the increase in sample size to accommodate the planned interim analysis, 64 evaluable patients per group will provide the desired power. More details of the power characteristics are shown under the Interim Analysis section. We will recruit 70 patients in each arm to accommodate a 5-10% dropout rate.

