6 DATA COLLECTION AND ANALYSIS

6.1 DATA COLLECTION

For each subject who meets inclusion criteria, a clinical report form (CRF) must be completed and signed by the investigator to certify that the data within each CRF are complete and correct according to data collection schedule (Appendix I). Every effort

should be made to respond to all questions on each CRF page, completion of the data is required by the protocol. The header section of each CRF page should be completed to identify the Investigators/surgeon and subject identification.

Upon receipt of completed CRFs and prior to entering data into the aggregate data summary table, the site-coordinator will ensure the accuracy of data recorded by comparison to supporting source documents. Adherence to proper recording of information as well as assuring that corrections are being made will also be addressed.

One interim analysis will be conducted when the first half of patients in each group (35 treatment and 35 control) complete their 30-day follow-up visit. Specifically, the interim analysis will be blinded and conducted at a nominal 0.0031 one-sided level of significance, while the final analysis will be conducted at a nominal 0.0219 one-sided level of significance. These values were calculated using a third-degree Kim-DeMets power alpha-spending function evaluated at the halfway point. If the actual information fraction at the time of the analysis is different, or the DSMC requests additional unblinded analysis, the significance levels will be adjusted using the alpha-spending function.

Results of the interim analysis will determine if it is futile to continue patient enrollment based on statistically significant differences (24 hour decrease in the time to return of bowel function in the treatment group compared to controls at a one-sided 2.5% significance level between the treatment and control groups). In addition, the MCW IRB in collaboration with the study investigators may terminate the study at any time to maintain patient safety.

The following table shows the probability of early stopping and the overall power of the study for various hypothetical effect sizes. If the design assumptions are correct, the study will stop early for efficacy with 23% probability, but if the actual effect is 50% larger (due to larger mean difference or smaller within-group standard deviation), then the trial will stop early 60% of the time.

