6.3 DATA / STATISTICAL ANALYSIS

All efficacy analyses will be intent to treat. The time to bowel function recovery and hospital length of stay will be compared between the two groups using Student's t-test. Due to the short-term nature of the outcome measures we expect no censoring.

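### Recovery and stay partly reflect physicians' ordering decisions, but the planned t-test makes no use of the recorded surgeon: a modest, cheap gain in precision forgone, not a bias

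*Combined protocol and SAP*

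**What the plan says.** The primary objective (3.1.1) evaluates the drug "in conjunction with a standardization postoperative care pathway". Section 5.3 describes that pathway and leaves several steps open:

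- Release from NPO has default symptom criteria, but "Alternatively, clinical determination made by the physician can be utilized for diet advancement". The reason for a departure must be recorded.
- After clear liquids there is no default: "Diet advancement after clears will occur at physician discretion".
- Non-narcotic adjuncts are the physician's choice.
- Discharge has minimum criteria only, one of which is tolerating a diet beyond clears.

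Section 3.2.1.1 counts toleration of liquid diet, solid diet and oral pain medication, GI-2 and GI-3 among the recovery measures. Solid food is part of both GI-2 and GI-3. Length of stay (3.2.2.1) ends when the discharge order is written.

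Sections 4.4.2 and 5.3 describe one list, prepared in advance under a randomization plan and used in order of enrollment. No stratification factor is named. On data capture, section 6.1 says "The header section of each CRF page should be completed to identify the Investigators/surgeon and subject identification". On analysis, section 6.3 says "The time to bowel function recovery and hospital length of stay will be compared between the two groups", by Student's t-test and with no covariate.

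**The concern.** A patient cannot tolerate solid food before someone orders it, and cannot leave before someone writes the discharge order. Where physicians differ in how early they do these things, the difference enters the outcome but has nothing to do with study drug. An unadjusted two-group test leaves it in the error term. With a list not known to be balanced by surgeon, it also adds chance variation to the estimated treatment difference.

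The stake is efficiency. The design has little slack: 70 per arm with 10% dropout leaves 70 × 0.90 = 63 evaluable, against the 64 required. A variable that is already recorded and fixed before the outcome could recover some precision without extra patients. The choice is credible only if made before unblinding, since adding surgeon afterwards would look data-driven.

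**Working it through.** **Inputs from the documents.** Section 4.3.3 gives "at least 80% power to detect a 24-hour decrease in the time to return of bowel function" and "we expect a standard deviation of 48 hours", tested "at a one-sided 2.5% significance level. This corresponds to a two-sided 5% significance level", with 64 evaluable per group. Section 6.1 gives one interim look at half the information with a third-degree power spending function, and its table note calls the 48 hours a within-group standard deviation.

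**Inputs assumed.** The share s of outcome variance that lies between surgeons (0 to 0.20) and the number of surgeons (3 or 6). Neither is in the documents.

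**1. The plan's own figure.** Alpha spent at the interim is 0.025 × 0.5³ = 0.003125, so the first boundary is z = 2.734. Solving for a total of 0.025 gives a second boundary of z = 1.983. The expected final z is (24/48) × √(64/2) = 2.828, and at the interim 2.828 × √0.5 = 2.000. Stopping probability at the interim is 1 − Φ(2.734 − 2.000) = 23.1% (stated 22.9%). Overall power is 80.4% (stated 80.0%). The plan's figure reproduces.

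**2. Adjusting for surgeon, normal approximation.** Take 48 h as the total SD. The residual SD is 48 × √(1 − s), the expected final z is 2.828/√(1 − s), and the equivalent increase in sample size is 1/(1 − s) − 1.

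| s | Residual SD (h) | Power at 64 per arm | n per arm for 80% | Equivalent extra patients |
|---|---|---|---|---|
| 0 | 48.0 | 80.4% | 63.4 | 0% |
| 0.05 | 46.8 | 82.3% | 60.3 | 5% |
| 0.10 | 45.5 | 84.3% | 57.1 | 11% |
| 0.20 | 42.9 | 88.2% | 50.7 | 25% |

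This ignores the degrees of freedom spent on surgeon and uneven arm numbers within surgeon, so it is an upper figure.

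**3. Simulation allowing for those costs** (single look, unstratified list, 64 per arm, equal-volume surgeons, total SD held at 48 h). Gains in power at s = 0.05, 0.10 and 0.20 were about 1.7, 3.7 and 7.8 points with 3 surgeons, and 0.5, 2.3 and 7.3 with 6. At s = 0 adjustment lost about 0.5 to 2 points. A repeat with 40,000 trials per setting agreed to within about 0.7 of a point.

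**4. Sensitivity to what the share means.** If surgeon effects are instead drawn at random with long-run share 0.20, a few surgeons realise only part of it. With 3 surgeons the average is (2/3) × 0.20 = 0.133, and the total SD falls to 48 × √(0.80 + 0.133) = 46.4 h. The unadjusted test then does better and the gain is smaller: 83.44% to 87.83% (4.4 points) with 3 surgeons, 81.41% to 86.85% (5.4 points) with 6.

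**5. Validity of the planned test.** Its simulated one-sided type I error was 0.024 to 0.028 against 0.025. The chance shift from surgeon imbalance has SD of about 48 × √s × √(2/64), which is 2.7 h at s = 0.10. The standard error of the unadjusted difference, 48 × √(2/64) = 8.5 h, already contains it.

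**The case against.** The strongest reply is that nothing here is an error. The t-test holds its level, discretion is exercised blind to arm, and the sample size reproduces. If the 48 hours, taken partly from internal data, includes differences between surgeons, they are already paid for. All of that stands. A reader might infer that the comparison is biased, or that a chance imbalance by surgeon invalidates it. Step 5 shows otherwise.

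A reader might also infer that the trial is underpowered. That would need 48 h to be a within-surgeon SD, in which case the planned test would have 78.3%, 76.1% or 71.1% power at shares of 0.05, 0.10 and 0.20. The documents call it a within-group SD and nowhere split it by surgeon, so they do not support that reading.

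Four further limits stand:

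- Release from NPO is not simply left to the physician. Criteria are the default and departures must be justified. Discretion is complete only after clears.
- The randomization plan is cited but not set out. One can say that no stratification is described, not that the list ignores surgeon.
- Section 5.3 gives these decisions to the physician, while the CRF header identifies the investigator or surgeon. Surgeon is therefore a proxy for whoever wrote the order and may capture only part of the variation.
- The 24 h and 48 h inputs are for return of bowel function. First flatus and first bowel movement are patient-reported and less open to ordering habits. No SD is given for length of stay, so its gain cannot be computed separately.

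Nor do the documents support any particular share. This is one site with a shared pathway, and the true value may be near zero.

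**Conclusion.** The point holds as a recommendation for precision, not as a correction. The plan writes physician discretion into steps that feed solid-diet, GI-2, GI-3 and length-of-stay times, records the surgeon, and then does not use that information.

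With 64 per arm, 3 to 6 surgeons and a total SD of 48 h, the gain is about 0.5 to 2 points of power at an assumed 5% share, 2 to 4 at 10% and 7 to 8 at 20%. The last falls to about 4 to 5 if the 20% is a long-run share that a few surgeons only partly realise. The gain applies mainly to diet-dependent measures and stay. The planned test remains valid, and the stated power is not shown to be wrong.

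**What to change.** In section 6.3, before any unblinding, replace the two-group t-test for recovery time and length of stay with a linear model containing treatment and surgeon (from the CRF header) as fixed factors. Use the same model at the interim and the final analysis. Pool surgeons below a fixed count, for example fewer than 10 patients, into one category, with the grouping decided blind to outcome and arm. If enrollment is still open, have IDS stratify the remaining list by surgeon. No clinical care changes.

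The cost is a short amendment to 6.3, one degree of freedom for each surgeon category beyond the first, and some work by IDS if the list is stratified. No new data or patients are needed. The downside is about 0.5 to 2 points of power if several surgeons turn out not to differ. With a single surgeon the change has no effect.

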5.4 ADVERSE EVENT REPORTING

If your study collects patient specific safety data, provide timelines and a detailed description of procedures for collecting, assessing and reporting adverse events. A technical guide is available upon request to assist you in completing the following section.

It is the responsibility of the investigator(s) to oversee the safety of the study. The safety monitoring will include careful assessment and appropriate reporting of complications/events as noted below.

Adverse events will be reviewed for clinical relevance and cause relation and reported as the events occur.

The ACS NSQIP Variables and Definitions guidance document will be used to ensure consistency of defining and reporting the complications or events in this study.

5.4.1 DEFINITIONS

An adverse event (AE) is any untoward medical occurrence in a patient or clinical investigation subject administered a pharmaceutical product and which does not necessarily have a causal relationship with this treatment. An AE can therefore be any unfavorable and unintended sign (including an abnormal laboratory finding, for example), symptom, or disease temporally associated with the use of a medicinal product, whether or not considered related to the medicinal product.

Pregnancy is not an AE; however, if a female subject becomes pregnant during the conduct of the study, the Investigator should discontinue study medication immediately. Follow up information regarding the outcome of the pregnancy and any sequelae, including fetal or neonatal abnormalities should be obtained and documented. All information obtained about the pregnancy including information on the infant after birth should be forwarded to Cubist Pharmacovigilance as soon as possible.

The identification of the presence of a non-susceptible microorganism during treatment is generally not considered an AE unless associated with other unintended consequences (e.g., worsening of the disease under treatment).

5.4.2 RELATIONSHIP TO STUDY MEDICATION

Many terms and definitions can be used to describe the causal relationship between a drug product and an AE. Examples include: definitely, probably, possibly, unlikely related, or not related. Phrases such as “plausible relationship”, “suspected causality”, or “causal relationship cannot be ruled out” have also been used to describe a positive causal attribution between the product and the AE. There is currently no standardized nomenclature.

1. Not Related: an AE with a temporal relationship to the drug administered that makes a causal relationship improbable, and/or for which other drugs or underlying or concurrent disease provide a plausible explanation
2. Unlikely Related: an AE that has a plausible temporal relationship to the drug administered, but for which other causative factor(s) more likely account for the event and where dechallenge (withdrawal of drug treatment) or dose reduction was not felt clinically indicated or improvements on dechallenge or dose reduction have not been observed
3. Possibly Related: an AE that has a plausible temporal relationship to the drug administered, but for which other causative factor(s) could account for the event and where improvements on dechallenge or dose reduction may or may not have been observed.

5.4.3 EXPECTEDNESS OF AE

An AE is considered *unexpected* if the specificity or severity is not consistent with the applicable product information. In this case, where a study is being performed prospectively outside of the current labeled use (e.g., the investigator holds their own IND), the Investigator Brochure is considered the applicable product information.

Warnings and precautions as provided in the prescribing information packet include:

1. A higher number of myocardial infarctions was reported in patients treated with alvimopan 0.5 mg twice daily compared with placebo 12 in a 12-month study in patients treated with opioids for chronic pain, although a causal relationship has not been established

2. Patients recently exposed to opioids are expected to be more sensitive to the effects of ENTEREG and therefore may experience abdominal pain, nausea and vomiting, and diarrhea.
3. Not recommended in patients with severe hepatic impairment.
4. Not recommended in patients with end stage renal disease.
5. Most common adverse reaction (incidence >1.5%) occurring with a higher frequency than placebo among ENTEREG-treated patients undergoing surgeries that included a bowel resection was dyspepsia.
6. Not recommended in patients with complete GI obstruction or in patients who have surgery for correction of complete bowel obstruction.
7. Not recommended in pancreatic or gastric anastomosis.

5.4.4 RECORDING AND REPORTING AN AE

If AEs are collected, any AE, regardless of seriousness, severity, or causal relationship to a drug, should be recorded on the case report form or SAE form. For retrospective studies, investigators should report all AEs identified during the study period defined in the protocol.

Any AE, regardless of seriousness, severity, or causal relationship to the study medication, will be recorded on the case report form or SAE form. The form contains fields that allow for complete evaluation of an AE. All AEs starting with the first intervention or dose of study medication and throughout the duration of the study (through last patient visit) will be monitored.

5.4.5 RECORDING AND REPORTING A SAE

5.4.5.1 STUDIES NOT PERFORMED UNDER AN IND

Please report all required safety data to your IRB in accordance with your IRB's directions. Healthcare professionals are encouraged to report adverse events or side effects related to the use of these products to the FDA's MedWatch Safety Information and Adverse Event Reporting Program; online reporting is available via: www.fda.gov/MedWatch/report.htm. On the same day that you notify the FDA or your IRB, please send a copy of the AE report that you have submitted to the FDA or your IRB to Cubist's Pharmacovigilance department at [contact]. You will also be expected to cooperate with Cubist regarding any safety related inquiries related to this report.

Not Applicable.

5.4.5.2 STUDIES PERFORMED UNDER YOUR OWN IND

You are obligated to notify the FDA in a written IND Safety Report of any adverse experience that you assess as both serious and related to the drug and are unexpected no later than 15 calendar days after your initial receipt of the information. Please refer to 21 CFR Part 312.32 for definitions and reporting timeframes and requirements.

Please report all required safety data to your IRB in accordance with your IRB's directions.

On the same day that you notify the FDA of any SAE you must send a copy of each IND Safety Report (Initial Written Report and any Follow-ups to a Written Report) to Cubist's Pharmacovigilance department at [contact]. You will also be required to cooperate with Cubist regarding any safety related inquiries.

Recording of AEs

Any AE, regardless of seriousness, severity, or causal relationship to a drug, will be recorded on the case report form or SAE form. The form contains fields that allow for complete evaluation of an AE. All AEs starting with the first intervention or dose of study medication and throughout the duration of the study (through last patient visit) will be monitored.

Reporting of SAEs

The study team will notify the FDA in a written IND Safety Report of any adverse experience that is assessed as both serious and related to the drug and is unexpected (not previously described in the package insert or Investigator's Brochure). Each notification shall be made no later than 15 calendar days after initial receipt of the information. 21 CFR Part 312.32 will be referenced for definitions and reporting timeframes and requirements.

Written notification using a MedWatch form (Form FDA 3500A) will be submitted or in narrative format. The submission will be clearly marked with the studies assigned IND number and "IND Safety Report". In each written IND Safety Report, the study team will identify all safety reports (if any) previously filed with the IND concerning similar adverse experience, and will analyze the significance of the adverse experience in light of the previous, similar reports.

The study team is obligated to notify the FDA by telephone or FAX of any unexpected fatal or life-threatening experiences assessed as related to the drug no later than 7 calendar days after initial receipt of the information. The telephone call or FAX will be made to the Regulatory Project Manager at the study teams FDA review division. The telephone/FAX notification will be followed by a written IND Safety Report within 15 days of your initial receipt.

The study team is also, obligated to promptly investigate all safety information and submit follow-up information to an initial written report (IND Safety Report—Follow-up to a Written Report) as soon as relevant information is available.

On the same day that you notify the FDA, the study team will send a copy of each IND Safety Report (Initial Written Report and Follow-up to a Written Report) to Cubist. Copies of the IND Safety Report will be sent to Cubist Pharmacovigilance via email or FAX. Email: [contact] [contact]

In the cover letter to Cubist, the study team will identify ourselves as a Sponsor-Investigator, provide our assigned IND number, full contact information, protocol title, and when the report was sent to the FDA.

